Glucose meter and insulin rate reporting: The research assistant will provide instructions for the participant to report readings from their diabetes devices. For continuous glucose sensor and insulin pump users, device data for the past month will be provided through data exports from the device software for sharing with healthcare teams, with no medical device ID or personal identifiers retained. For glucose meter users, they will report glucose readings for the last 7 days from their glucose meter. For insulin injection users, they will report long-acting insulin doses and carbohydrate exchange ratios used over the last 7 days.

As the final activity of the baseline assessment, the participants will be randomized to the Activate program or treatment-as-usual and receive instruction, if required on completing the intervention program, and for all the follow-up assessment.

After twelve weeks, adolescents and their primary caregiver will repeat the entire baseline assessment battery in a second video-based lab appointment. Adolescents will receive \$25 for the intake assessment and \$50 for the follow-up assessment on a study provided cash card or gift card. Adolescents will return the assessment toolkit with a pre-paid mailing label.

Intervention: Activate Program

Adolescents randomized to the active condition will participate in a 12-week online diabetes behavior-change skills training and physical activity promotion program. See attached intervention guide for protocols beyond description below.

Diabetes Behavior-Change Skills Training. Behavior-change skills training will be provided through eight web-delivered content and activity sessions across the 12-week program. Sessions 1 through 4 will occur weekly and sessions 5 through 8 biweekly. Each session takes approximately 15-20 minutes for the adolescent to complete both content learning and related activities. Session 1 (week 1 of program) provides an introduction to the entire Activate Program as well as a goal-setting activity related to type 1 diabetes management. Sessions 2-8 (weeks 2 to 12 of the program) provide physical activity reminders that overlap with text-based support for the physical activity program (see below) as well as specific session content for behavior-change skills training: goal setting, goal planning and rewards, identifying challenges, problem-solving, increasing social support and positive activities, and managing strong emotions.

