Behavior-Change Skills. We will use two measures to assess key behavior-change skills taught in the intervention program: goal setting and coping skills. Adolescents' goal setting will be assessed using a procedure by Karoly et al. (2005) that was validated for use with adolescents with type 1 diabetes.^{65,66} Participants will be asked to identify their most important diabetes, academic, social, and career/family goals. Following this, participants will be asked to identify which of their three non-diabetes goals most interfered with their diabetes goal. Participants will also complete the four-item planning subscale from the Goal System Assessment Battery⁶⁵ to determine goal-directed planning activity related to the diabetes goal identified in the goal assessment. Average levels of goal-directed planning will be used as the outcome variable for goal setting. Adolescents' coping skill self-efficacy will be assessed using the Coping Self-Efficacy Scale, a 26-item measure that indexes participants confidence in using different strategies to cope with challenges in daily life.⁶⁷

Active minutes. We will use Garmin fitness activity tracker tracking to determine the average number of daily minutes with moderate to vigorous physical activity, metabolic equivalents (METs) greater than or equal to 3 METs, in week 1 and week 12.

Secondary Biobehavioral Self-Regulation Mechanisms

2. **Self-Report Assessment of Behavior Regulation and Distress:** The self-report tasks will be completed via questionnaires linked only to study ID on RedCap with the access link provided by the research assistant. When noted the parent will also report on their perception of their child's functioning in that domain.

Self-Regulation. We will use the following measures to assess regulation generally and in the diabetes context.

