****If genetic information is being collected, GINA language must be added to the consent form.**

*Deception typically involves withholding information from the potential subject and would require an alteration to the consent process.

Statistical Considerations: Delineate the precise outcomes to be measured and analyzed. Describe how these results will be measured and statistically analyzed. Delineate methods used to estimate the required number of subjects. Describe power calculations if the study involves comparisons. Perform this analysis on each of the primary and secondary objectives, if possible.

In aim 1, we assess the feasibility and acceptability of the Activate program as well as its preliminary efficacy on behavior-change skills (goal-setting and coping skill efficacy) and average daily active minutes. To assess acceptability of the Activate program we will examine participant engagement with the Activate program components, including behavior skill training sessions completed and physical activity goals met, as well as qualitative and quantitative participant feedback on their experience with the program at the end of treatment. A priori benchmarks for acceptability, indicating no further revision is needed will be greater than 80% of sessions completed and physical activity goals met as well as more than 80% of participants providing positive feedback regarding willingness to participate again.

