To assess the preliminary efficacy of the Activate program we will examine changes in proximal primary outcomes of goal-setting, coping skill efficacy, and average daily active minutes compared between treatment and control groups at baseline and the 12-week follow-up assessment. We will conduct multilevel models with baseline-residualized gain scores for outcomes to identify the effect size for the treatment program on each of the three primary outcomes. Each model will include the baseline outcome covariate as well as additional disease covariates including diabetes technology use and length of diagnosis. All participants will be used in analyses, with missing data addressed with full information maximum likelihood estimation. A power sensitivity function was generated wherein our pilot study analyses were used to determine expected effect sizes. Anticipated effect sizes based on our pilot work for between group differences in behavior-change skills and average daily active minutes are Cohen's d of 0.4 to 1.2. With 60 participants, we will have 80% power to detect a Cohen's d of .7, 60% power to detect a Cohen's d of .6, at 95% power to detect a Cohen's d of .8. Thus, we will be powered to detect all but the smallest of potentially meaningful effects found in our previous intervention pilot work.

In aim 2, we test the impact of the Activate program on secondary mechanisms of biobehavioral self-regulation systems and glycemic and cardiovascular disease risk outcomes closely linked with type 1 diabetes health disparities. To assess changes in putative mechanisms and secondary outcomes we will use baseline-residualized gain scores in multilevel models to identify the effect size for the treatment program on each of the secondary outcomes assessed for behavior regulation, distress, c-reactive protein, mean and variability in daily blood glucose, and cardiovascular disease risk score. For all analyses missing data will be addressed with full information maximum likelihood estimation. A power sensitivity function was generated wherein our pilot study analyses were used to determine expected effect sizes. Based on our pilot work we anticipate effect sizes from Cohen's d of .4 to .8 and thus with 60 participants, we will again have 80% power to detect a Cohen's d of .7, 60% power to detect a Cohen's d of .6, at 90% power to detect a Cohen's d of .8. We will be powered to detect all but the smallest of potentially meaningful effects found in our pilot work.

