Should any adverse events, unanticipated problems or reportable new information arise, the PI will contact the IRB according to the Adverse Event and Unanticipated Problems Reporting Policy using the UVM Reporting Form.

Withdrawal Procedures: Define the precise criteria for withdrawing subjects from the study. Include a description of study requirements for when a subject withdraws him or herself from the study (if applicable).

At any time, a participant can choose to withdraw from participation. We do not anticipate withdrawing any adolescent from the study but reserve the right to do so under unforeseen circumstances. These might include situations such as discovery of a medical problem indicating the adolescent should not participate in physical activities. If a participant is withdrawn or withdraws from participation their data will not be included in analyses.

Sources of Materials: Identify sources of research material obtained from individually identifiable human subjects in the form of specimens, records or data. Indicate whether the material or data will be obtained specifically for research purposes or whether use will be made of existing specimens, records or data.

All data is being collected solely for research purposes. Participants will provide dried blood spot assays, measurements of abdominal circumference and blood pressure as well as complete computerized self-report questionnaires. This data will be coded at the time of collection.

DRUG INFORMATION

Investigators are encouraged to consult the UVM Medical Center Investigational Pharmacy Drug Service ([name]) prior to finalizing study drug/substance procedures.

Drug (s)

Not applicable

Drug name – generic followed by brand name and common abbreviations. Availability – Source and pharmacology; vial or product sizes and supplier. If a placebo will be used, identify its contents and source.

Preparation: Reconstitution instructions; preparation of a sterile product, compounded dosage form; mixing guidelines, including fluid and volume required. Identify who will prepare.

Storage and stability – for both intact and mixed products.

Administration – Describe acceptable routes and methods of administration and any associated risks of administration.

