#### Statistical Analysis Plan:

To assess the preliminary efficacy of the Activate program we will examine changes in proximal primary outcomes of average daily active minutes compared between treatment and control groups at baseline and the 12-week follow-up assessment. We will conduct multilevel models with baseline- residualized gain scores for outcomes to identify the effect size for the treatment program on each on the primary outcome. All participants will be used in analyses, with missing data addressed using an intention-to-treat approach where missing data were included and given a zero. A power sensitivity function was generated wherein our pilot study analyses were used to determine expected effect sizes. Anticipated effect sizes based on our pilot work for between group differences in behavior-change skills and average daily active minutes are Cohen's  $d$  of 0.4 to 1.2. With 60 participants, we will have 80% power to detect a Cohen's  $d$  of .7, 60% power to detect a Cohen's  $d$  of .6, at 95% power to detect a Cohen's  $d$  of .8. Thus, we will be powered to detect all but the smallest of potentially meaningful effects found in our previous intervention pilot work.

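### The protocol removes withdrawn participants' data from the analyses, although the aim 1 analysis and the SAP's intention-to-treat analysis both use every participant

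*Protocol*

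**What the plan says.** The protocol's Withdrawal Procedures section lets a participant leave at any time and reserves the team's right to withdraw someone, for example after a medical finding that rules out exercise. It then states: "If a participant is withdrawn or withdraws from participation their data will not be included in analyses".

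Three other statements bear on the same person:

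- Protocol, Statistical Considerations, aim 1 (the primary outcomes): "All participants will be used in analyses, with missing data addressed with full information maximum likelihood estimation".
- Protocol, Statistical Considerations, aim 2: "For all analyses missing data will be addressed with full information maximum likelihood estimation". This paragraph gives a missing-data method but no statement of who is analysed.
- SAP, on active minutes: "All participants will be used in analyses, with missing data addressed using an intention-to-treat approach where missing data were included and given a zero".

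On timing, the protocol's Procedures section says: "As the final activity of the baseline assessment, the participants will be randomized to the Activate program or treatment-as-usual". The follow-up visit is described as: "After twelve weeks, adolescents and their primary caregiver will repeat the entire baseline assessment battery in a second video-based lab appointment". Active minutes come from the tracker and are averaged over activity "greater than or equal to 3 METs, in week 1 and week 12".

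For acceptability, Statistical Considerations sets a benchmark of "greater than 80% of sessions completed and physical activity goals met". Reaching it is taken to mean that the programme needs no further revision. The set of participants over whom it is computed is not stated.

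**The concern.** An analyst with a randomised participant who later withdraws has three instructions: drop the person, keep the person under FIML, or keep the person with zero for whatever is missing. They cannot all be followed. If the choice is made once data are in hand, the analysis set is no longer pre-specified.

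Dropping the person is also not the intention-to-treat analysis that the SAP names. Those removed include participants whom the team withdraws, so the exclusion is not confined to families who no longer want their data used.

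Two further things are at stake. Outcome data already collected could be thrown away. And if the word analyses covers the acceptability benchmarks, those who formally withdraw would vanish from the figures used to decide whether the programme needs revision, although their leaving is itself evidence on acceptability.

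**Working it through.** **1. Is the exclusion after randomisation?** Randomisation is the last step of the baseline visit, and withdrawal is allowed at any time. Any withdrawal in the 12 weeks that follow therefore concerns a randomised participant. No statement limits the analysed set to those who stay.

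**2. What happens to one withdrawn participant under each text?**

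| Source | In the analysis? | Missing week-12 value |
|---|---|---|
| Protocol, Withdrawal Procedures | No | Not applicable |
| Protocol, aim 1 | Yes | FIML |
| Protocol, aim 2 | Not stated | FIML |
| SAP, active minutes | Yes, intention-to-treat | Set to zero |

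**3. Can a recorded primary outcome be lost?** Yes. The tracker supplies active minutes in week 12, and the visit comes after twelve weeks. Someone who withdraws between the two has an active-minutes outcome that the withdrawal rule discards. Goal planning and coping self-efficacy are collected at the visit, so that person has no follow-up value for them.

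**4. Does the choice matter when there is no week-12 outcome?**

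- Exclusion against FIML: little. In a model of the outcome given arm and baseline value, a person without the outcome adds essentially nothing to the estimate of the arm effect.
- Exclusion against the SAP's zero rule: it can matter. If k of 30 in an arm are scored zero and the rest average m, the arm's raw mean is m × (30 − k)/30, a fall of k/30. With an assumed k = 3 this is 3/30 = 10%.

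**5. Session benchmark, illustration only.** From the documents: 8 sessions, and a threshold of more than 80%. Assumed: 30 in Activate (half of 60), sessions pooled over participants, k withdrawals each with s sessions done, and those who stay averaging t sessions.

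- Over all randomised: completion = (s × k + t × (30 − k)) / (8 × 30).
- Withdrawals excluded: completion = t / 8, whatever k is.

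With t = 7, s = 0 and k = 3: (0 + 7 × 27) / 240 = 189 / 240 = 78.75%, which misses the benchmark. With the three excluded: 189 / (8 × 27) = 189 / 216 = 87.5%, which meets it.

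The benchmark is missed when completion is 80% or below, that is when k ≥ (30t − 192) / (t − s). The smallest such k is:

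| Stayers' average (figure with withdrawals excluded) | s = 0 | s = 2 | s = 5 | s = 6 |
|---|---|---|---|---|
| 8 of 8 (100%) | 6 | 8 | 16 | 24 |
| 7 of 8 (87.5%) | 3 | 4 | 9 | 18 |
| 6.5 of 8 (81.25%) | 1 | 1 | 2 | 6 |

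The range runs from 1 to 24 of 30 and is driven mainly by how many sessions the stayers complete. The documents give neither a withdrawal rate nor a session completion rate, so the table shows the mechanism and not a forecast.

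**The case against.** The sentence may be meant only to honour families who take back permission to use their data. The consent pages are not available, so this cannot be checked. But the sentence does not say so, and it equally covers participants whom the team withdraws. The replacement below still lets a family have its data removed.

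A reader might infer that the benchmarks could never register people drifting away. The documents do not support that. The rule covers formal withdrawal only. An adolescent who stops doing sessions or misses the follow-up visit without withdrawing is not excluded by it and would still lower completion. It is also an inference that the word analyses extends to these descriptive figures. What stands is that their denominator is undefined.

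The loss of a recorded primary outcome needs withdrawal in a narrow window, and only active minutes are affected. That is fair: it shows that the rule can discard good data, not that it often will.

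On adverse events, a reader might infer that they would go unrecorded. They would not. The monitoring plan provides for documenting events for each participant, reporting to the ethics board and review by an independent medical monitor. Read literally, the rule touches only the planned comparison between arms.

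**Conclusion.** The contradiction is real and rests on the text alone. The withdrawal rule removes randomised participants, whereas the aim 1 analysis and the SAP keep them. Following the rule as written would not give the analysis that the SAP names. It should be corrected.

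A reader might go further and conclude that the efficacy estimate is biased or loses power. The documents do not support this: they give no number of withdrawals, no rate by arm and no reason to expect a particular direction. Unequal removal by arm is possible, not shown.

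Nor should a reader assume that correcting the rule leaves the efficacy estimate almost unchanged in every case. For those with no week-12 outcome, that is so only if missing data are handled by FIML. Under the SAP's zero rule the same people would move from excluded to zero active minutes.

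The one figure offered, 78.75% against 87.5%, depends on the assumptions of 30 in Activate, pooled sessions, stayers at 7 of 8, three withdrawals at zero sessions, and the rule reaching the benchmarks at all.

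**What to change.** Replace the sentence in Withdrawal Procedures with: *Participants who withdraw or are withdrawn stay in the arm to which they were randomised, and all data collected up to that point are analysed, unless the family asks for their data to be removed.* Put matching text in the SAP, and in the consent form if needed.

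In addition:

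- State that the session and goal benchmarks are computed over all participants randomised to Activate.
- Report withdrawals by arm.
- Keep withdrawn participants' recorded adverse events in the summary by arm.
- Make this change together with reconciling the protocol's FIML rule and the SAP's zero rule. That conflict is a separate point, but it decides what retaining withdrawn participants does to the active-minutes result.

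The cost is wording. No new data and no larger sample are needed. The acceptability figures may come out slightly less favourable.

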All procedures will be conducted solely for research purposes. We will recruit 60 adolescents aged 13-17 years old with type 1 diabetes, through pediatric endocrinology clinics and via a national advertising recruitment method established with our research team that leverages Facebook, Instagram, and Google Ads resulting in a nationally representative sample. National advertising recruitment: Interested families will contact the research team. Pediatric endocrinology clinic recruitment: A clinic staff member will provide the same online information used in national recruitment about the study to the family during a clinic visit and interested families will be provided with instructions for how they can contact the research team if interested in participating. At the University of Vermont Medical Center pediatric endocrinology clinic, a member of the patient's care team will ask eligible families for permission to have one of our research team members enter to share our same recruitment flyer used in national recruitment about the study and instructions for how they can contact the research team if interested. Research staff will respond to interested families and explain the study procedures in greater detail to the adolescent and to the adolescent's legal guardian. If both agree, the research assistant will arrange for a call to complete the electronic informed consent and assent process through RedCap. After consent/assent, the adolescent and parent will complete the baseline video-based lab assessment and be mailed an assessment kit with all required tools for the assessment and program (dried blood spot assays, Garmin fitness activity tracker, measuring tape, electronic blood pressure cuff, scale). Families without a computer, tablet, or phone, will be provided a small tablet to use for assessments.

The baseline assessment will be conducted with the ongoing support of the research staff via a video conference using Larner College of Medicine Zoom with HIPAA-compliant settings and the parent available at home. There will be no video recording. First, the adolescent and parent will complete a set of online questionnaires (through RedCap), see descriptions below of measures. Second, the adolescent will complete the physical assessments:

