Contact between potential participants and study personnel will be initiated by the potential participants and their caregivers. Potential participants and their caregivers will respond to internet or clinic-provided advertisements and will be routed to our study website. Our study website will contain a description of study procedures and link to request contact regarding study participation. A research assistant will return contact with interested families to answer questions about the study and confirm eligibility using the screening consent script and set a date/time for consent/assent. Inclusion criteria will be the adolescents aged 13-17, and not turning 18 during study participation, with type 1 diabetes, being at least 18 months post-diagnosis, parent reported moderate to no physical activity for adolescent, ability to complete measures and intervention program in English, and access to broadband or cellular internet and currently residing in and receiving healthcare in the United States. After 30 participants are consented and enrolled into the study, we will add the following inclusion criteria: adolescent is from a marginalized racial or ethnic group. Exclusion criteria will be ward of state, active psychosis, and/or severe medical or psychiatric illness that limit participation including participation in physical activity. Participants will be provided contact information for the PI and lab to communicate during the 12-week study period about any concerns for eligibility (e.g., loss of internet, change in legal guardian status) and the PI will evaluate continued participation based on confirmation of meeting eligibility requirements.

For research involving survey, questionnaires, etc.: Describe the setting and the mode of administering the instrument and the provisions for maintaining privacy and confidentiality. Include the duration, intervals of administration, and overall length of participation.

Not applicable

Each assessment will be scheduled for a three-hour window to complete the questionnaires (80 minutes), the physical assessments (dried blood spot, abdominal circumference, blood pressure, and diabetes device reporting; 40 minutes), and at intake introduction to the treatment condition (20 minutes). Each assessment appointment is anticipated to last 2.5-3 hours.

Primary Outcomes

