This study examines an intervention to reduce health disparities for adolescents with type 1 diabetes and socioeconomic disadvantage. Our goal is to recruit a heterogeneous sample of families with and without SED to achieve a comparison of this intervention's feasibility with adolescents with type 1 diabetes and SED. We will recruit 60 adolescents aged 13-17 years old with type 1 diabetes, through a mixed clinic-based and national advertising recruitment method established with our research team that leverages Facebook, Instagram, and Google Ads resulting in a nationally representative sample (see attached advertisement). We believe these recruitment strategies will allow us to obtain a heterogeneous sample. Inclusion criteria will be the adolescents being at least 18 months post-diagnosis (due to a "honeymoon" period for glycemic outcomes in the first year after diagnosis), parent reported moderate to no physical activity for adolescent, ability to complete measures and intervention program in English, access to broadband or cellular internet, and currently residing in and receiving healthcare in the United States. In order to recruit a heterogeneous sample that aligns with our research goals, we will modify our recruitment criteria after we have enrolled 30 participants in the study. This modification will include the addition of the following inclusion criteria: adolescent is from a marginalized racial or ethnic group. Exclusion criteria will be ward of state, active psychosis, severe medical or psychiatric illness that limit participation (including any contraindications for physical activity per parent report on the physical activity readiness questionnaire). We are specifically recruiting adolescents aged 13-17 with type 1 diabetes and socioeconomic disadvantage due to the specific developmental challenges associated with disease management during this developmental period and the importance of this period for reducing future health disparities.

Vulnerable Populations: Explain the rationale for involvement of subjects (e.g., cognitively impaired, Non-English speaking, prisoners, students). Discuss what procedures or practices will be used in the protocol to minimize their susceptibility to undue influences and unnecessary risk (physical, psychological, etc.).

Not applicable

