Inclusion/Exclusion Criteria: Eligibility and ineligibility criteria should be specific. Describe how eligibility will be determined and by whom. Changes to the eligibility criteria at a later phase of the research have the potential to invalidate the research.

Inclusion criteria will be the adolescents aged 13-17 years old with type 1 diabetes, at least 18 months post-diagnosis, parent reported moderate to no physical activity for adolescent, ability to complete measures and intervention program in English as well as access to broadband internet with a computer, tablet, or smartphone, and currently residing in and receiving healthcare in the United States. After 30 participants are enrolled into the study, inclusion criteria will also include that the adolescent is from a marginalized racial or ethnic group. Exclusion criteria will be ward of state, active psychosis, and/or severe medical or psychiatric illness that limit participation for the youth (including any contraindications for physical activity per parent report on the physical activity readiness questionnaire).

Eligibility will be determined during the recruitment process by the research team member using self-report of the parent and adolescent.

Inclusion of Minorities and Women: Describe efforts to include minorities and women. If either minorities or women are excluded, include a justification for the exclusion.

We will ensure representative inclusion of persons of color, women (13-17 years old), and people with socioeconomic disadvantage through our national recruitment method that includes recruitment in communities that share these characteristics. In addition, to ensure we are enrolling participants from minority groups, we will modify our eligibility criteria after we enroll 30 participants in the study, to enroll only persons of color.

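### Eligibility narrows by race or ethnicity for the second half of the sample, but neither the randomisation, the models nor the claim of national representativeness reflects it

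*Protocol*

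**What the plan says.** The total sample is 60 (Protocol, Objectives and Study Design). The eligibility change appears in three places:

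- Inclusion/Exclusion Criteria: "After 30 participants are enrolled into the study, inclusion criteria will also include that the adolescent is from a marginalized racial or ethnic group".
- Subject Selection: "we will modify our recruitment criteria after we have enrolled 30 participants in the study". The reason given there is "In order to recruit a heterogeneous sample that aligns with our research goals".
- The screening text under Procedures, where the trigger is "After 30 participants are consented and enrolled into the study".

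Inclusion of Minorities and Women restates the aim from that point on as "to enroll only persons of color".

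Randomisation is covered in one sentence under Procedures: at the end of the baseline assessment "the participants will be randomized to the Activate program or treatment-as-usual". No ratio, list, block or stratum is named.

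Under Statistical Considerations, the Aim 1 models use baseline-residualized gain scores, with the baseline outcome, diabetes technology use and length of diagnosis as covariates. The SAP keeps the residualized gain scores and names no further covariate. Neither document mentions enrolment phase or race/ethnicity as a model term.

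Procedures and Subject Selection both describe recruitment as "resulting in a nationally representative sample". Methodological Innovation makes the same claim. In Subject Selection it stands in the same paragraph as the restriction.

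**The concern.** By design the two halves of the trial come from different eligible populations. The date of the switch is under the team's control and each participant's phase is known before randomisation. A variable of that kind is normally balanced in the allocation, entered in the model, or both. Here neither is planned, so any difference in outcome between the phases goes into residual variation and, in an unlucky allocation of 60 people, into the observed difference between arms.

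The representativeness wording matters separately. A reader of the results would take it as grounds for generalising to adolescents with type 1 diabetes nationally, and a sample whose second half is selected by race or ethnicity does not give those grounds.

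**Working it through.** **Inputs.** From the documents: N = 60, change after 30, stated power of 80% at d = 0.7. Assumed, because not stated: 1:1 allocation, two-sided alpha 0.05, 30 participants randomised in each phase, and an outcome difference D between phases of 0.3, 0.5 or 0.8 within-phase SD. The documents give no value for D.

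**1. The plan's power figure.** A two-sample t-test with 30 per arm gives 76% at d = 0.7 (normal approximation 77%), against the stated 80%. The stated figure is not reproduced under these assumptions. Adjustment for baseline could account for that one value. Nothing below depends on the 80%; 76% is the reference.

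**2. Chance imbalance in phase between arms.** The event is a gap of 20 percentage points or more in the share enrolled after the change, for example 18/30 against 12/30.

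- One random 30/30 split: the post-change count in one arm is hypergeometric (60, 30, 30). P(count ≤ 12 or ≥ 18) = 0.196.
- Coin toss: with X and Y independent Binomial(30, 0.5) for the post- and pre-change counts in one arm, P(|X/(X+Y) − (30−X)/(60−X−Y)| ≥ 0.20) = 0.155 by exact enumeration.
- Permuted blocks in order of enrolment, not stratified:
  - Sizes 2, 6 and 10 divide 30, so the gap is zero.
  - Size 4: the largest gap is 16/30 − 14/30 = 6.7 points.
  - Size 8: the largest gap is 18/32 − 12/28 = 56.3% − 42.9% = 13.4 points.
  - A 20-point gap did not occur in simulation for any of these sizes.

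**3. What such a gap would do in one realised trial.** Shift in a difference not adjusted for phase = gap × D. With a gap of 0.20 this is 0.06, 0.10 or 0.16 SD for D = 0.3, 0.5 or 0.8.

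**4. Precision lost by ignoring phase.** With equal halves the overall SD is √(1 + D²/4), so d = 0.7 shrinks to 0.7/√(1 + D²/4).

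| D | Overall SD | Effective d | Power ignoring phase | Loss against 76.0% |
|---|---|---|---|---|
| 0.3 | 1.011 | 0.692 | 75.1% | 0.9 points |
| 0.5 | 1.031 | 0.679 | 73.4% | 2.5 points |
| 0.8 | 1.077 | 0.650 | 69.7% | 6.3 points |

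This is before the planned baseline adjustment, which would remove part of any stable difference in level. Spending one degree of freedom on phase (57 instead of 58) leaves power at 76.0%.

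**5. Effects within a phase.** About 15 against 15 gives 46% power at d = 0.7.

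**6. Composition.** If a fraction p of the first 30 are from marginalized groups, the final share is 0.5 + 0.5p. For p of 20% to 50% (assumed) that is 60% to 75%, and by rule it cannot fall below 50%. The enrolment rule sets this share, and no target composition or weighting to a national population is given.

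**The case against.** The strongest reply is that nothing here biases the trial. The rule is prespecified, both arms recruit under it at all times, and allocation follows baseline. That stands. A reader might take the 0.10 SD in step 3 as a bias in the treatment effect. The documents do not support that: it is a chance shift in one unlucky allocation, it needs a phase difference for which they give no figure, and it ignores the baseline adjustment both documents plan. Ordinary standard errors already allow for chance shifts of this kind.

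A second reply is that the 16–20% depends on an allocation method the Protocol does not describe. That also stands: routine permuted blocks would remove the problem without anyone stratifying.

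The Inclusion/Exclusion section contains the sentence "Changes to the eligibility criteria at a later phase of the research have the potential to invalidate the research", from which a reader might infer that the trial is invalidated. This is instruction text on the institution's form. It does not make a pre-announced enrichment rule a defect, and enrichment is a legitimate aim.

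Phase is also only a proxy for group membership, since adolescents from marginalized groups can enrol in both halves. It is nevertheless the variable that the design itself creates, and it is recorded without error.

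Finally, the representativeness phrase is attached to the advertising method and no analysis uses it; enrichment might even offset under-recruitment of some groups. But the words describe the resulting sample, families volunteer in response to advertisements or clinic flyers, and the documents give no national composition against which to check the claim.

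**Conclusion.** The point holds as a cheap improvement in analysis and a needed correction of wording. It is not a threat to validity. The planned shift in population is absent from the randomisation text and from both sets of models. The consequence is a 16–20% chance of a 20-point phase imbalance if allocation is unrestricted, essentially none if it is blocked, and roughly 1 to 6 points of power at d = 0.7 for an assumed phase difference of 0.3 to 0.8 SD, less after baseline adjustment. These figures rest on 1:1 allocation, a two-sided 5% test and equal phases. The representativeness claim does not depend on them: it cannot stand beside a rule that restricts half the sample by race or ethnicity.

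**What to change.** 1. Add enrolment phase (before or after the eligibility change) as a prespecified covariate in the efficacy models of both the Protocol and the SAP. Define it by the criteria in force when the participant was consented, because the screening text ties the switch to consent and enrolment, while randomisation comes later. Cost: one degree of freedom.
2. If randomisation is not complete, use permuted blocks restarted at the change, and say so in the Protocol. Cost: a revised allocation list. If randomisation is complete, the covariate and the wording still apply.
3. Present any effects by phase as descriptive only.
4. In Methodological Innovation, Procedures and Subject Selection, replace the claim of national representativeness with *national volunteer sample enriched for marginalized racial or ethnic groups*. Cost: text edits.
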